1. PROTOCOL SUMMARY

1.1 Synopsis

Name of Sponsor: Visterra, Inc.				
Name of Investigational Intervention: VIS649				
Protocol Title:	A Multicenter, Randomized, Double-Blind, Placebo-Controlled, Multiple Dose Study to Evaluate the Efficacy and Safety of VIS649 in Participants with Immunoglobulin A (IgA) Nephropathy (IgAN)			
Short Title:	Phase 2 Study of VIS649 for IgA Nephropathy			
Rationale:	
VIS649 is a humanized immunoglobulin G (IgG₂) monoclonal antibody that binds to and blocks the biological actions of the cytokine A Proliferation Inducing Ligand (APRIL), a key factor in the production of aberrantly glycosylated IgA₁ (a-g- IgA₁), which is critical to the pathogenesis of IgAN. The central mechanism for the development of IgAN is the production of a-g IgA₁. These a-g IgA₁ act as autoantigens and trigger formation of autoantibodies forming circulating immune complexes which deposit in the mesangium of the glomeruli and trigger an inflammatory response and complement activation, causing damage to the kidneys.
 
In data from a single-ascending dose study of VIS649 in healthy volunteers, VIS649 reduced serum levels of IgA and a-g IgA₁. The current study will test the hypothesis that blocking the biological actions of APRIL in IgAN patients leads to reduction of serum IgA (including a-g IgA₁) levels and will reduce or halt the progression of IgAN, as measured by decrease in proteinuria.
 
The findings from this study will form the basis for subsequent clinical development of VIS649.
			
Objectives and Endpoints:	The key objectives and endpoints of the study are:			
	
  
 Primary Safety Objective	Primary Safety Endpoint	
   
  
 To evaluate the safety and tolerability of multiple, monthly doses of VIS649 at each of 3 dosing levels, administered IV to IgAN participants over the course of 12 months as an add-on to SOC treatment with ACEI/ARB therapy, compared with saline placebo infusions as an add-on to SOC treatment with ACEI/ARB therapy 	 
 AEs graded by severity, clinical laboratory tests, vital sign measurements, and physical examinations 	
  
	Primary Safety Objective	Primary Safety Endpoint	
 To evaluate the safety and tolerability of multiple, monthly doses of VIS649 at each of 3 dosing levels, administered IV to IgAN participants over the course of 12 months as an add-on to SOC treatment with ACEI/ARB therapy, compared with saline placebo infusions as an add-on to SOC treatment with ACEI/ARB therapy
Primary Safety Objective	Primary Safety Endpoint			

 To evaluate the safety and tolerability of multiple, monthly doses of VIS649 at each of 3 dosing levels, administered IV to IgAN participants over the course of 12 months as an add-on to SOC treatment with ACEI/ARB therapy, compared with saline placebo infusions as an add-on to SOC treatment with ACEI/ARB therapy 	
 AEs graded by severity, clinical laboratory tests, vital sign measurements, and physical examinations 			

	
Primary Efficacy Objective
 
 To evaluate the dose response of multiple, monthly doses of VIS649 on proteinuria at each of 3 dosing levels, administered IV to IgAN participants over the course of 12 months as an add-on to SOC treatment with ACEI/ARB therapy, compared with saline placebo infusions as an add-on to SOC treatment with ACEI/ARB therapy 	
Primary Efficacy Endpoint
 
 Change from baseline in uPCR (measured on natural log scale from 24-hour urine collection or the intended 24-hour urine collection) at Month 12 (ie, approximately 30 days after the twelfth dose is administered)

Secondary Objectives
 
 To evaluate the effect of repeated doses of VIS649 at 3 dosing levels versus placebo on the following parameters: 
 uPCR at Month 9 and 15 (ie, 4 months following the final [12th] monthly dose administration) 24-hour urine protein excretion at Months 9, 12, and 15 ≥ 30% decline from baseline in uPCR at Months 9,12, and 15 Clinical remission, defined as reduction in 24-hour urine protein excretion to < 300 mg/day for at least 3 consecutive months. eGFR at Months 12 and 15 To evaluate the effect of repeated doses of VIS649 at each dosing level compared with placebo on the following PD parameters: IgA, IgG, and IgM concentrations To determine the PK profile of repeated dose of VIS649, at each dosing level To determine the PK/PD profile of VIS649, relating VIS649 PK parameters and biomarkers such as 	
Secondary Endpoints
 
 Change from baseline in uPCR (measured on natural log scale from 24-hour urine collection or the intended 24-hour urine collection) at Months 9 and 15 Change from baseline in 24-hour urine protein excretion from baseline to Months 9, 12, and 15 Participants in each group achieving a ≥ 30% decline from baseline in uPCR at Months 9, 12, and 15 Participants in each group achieving clinical remission Change from baseline in eGFR at Months 12 and 15 Change from baseline in serum total IgA, IgG, and IgM concentrations at Months 9, 12, and 15 Serum PK parameters Correlation of VIS649 PK parameters with changes in IgA, uPCR, and eGFR 	

	
changes in IgA to changes in proteinuria and eGFR
 
 • To screen for ADA responses 	
 • Serum ADA levels

Abbreviations: ACEI = angiotensin-converting enzyme inhibitor; ADA = anti-drug antibody; AE = adverse event; a-g IgA = aberrantly glycosylated immunoglobulin A; APRIL= A PRoliferation Inducing Ligand; ARB = angiotensin receptor blocker; eGFR = estimated glomerular filtration rate; Ig = immunoglobulin; IgAN = immunoglobulin A nephropathy; IV = intravenous(ly); MEST = Mesangial cellularity, endocapillary proliferation, segmental sclerosis, tubular atrophy; PD = pharmacodynamic; PK = pharmacokinetic; SOC = standard of care; uACR = urinary albumin/creatinine ratio; uPCR = urinary protein/creatinine ratio.
		

Overall Design:
	
This is a Phase 2 multicenter, randomized, double-blind, placebo-controlled, multiple-dose study to evaluate the safety and efficacy of intravenously (IV) administered VIS649 over a 12-month treatment course in participants with IgAN. Participants will be enrolled from approximately 80 global sites in approximately 16 countries.
 
Screening evaluations, including physical examinations, vital signs, 12-lead electrocardiogram (ECG), safety laboratory testing (serum chemistry, hematology, urinalysis, serology, and pregnancy), and 24-hour urine collection, will take place approximately 30 days prior to the first dose of study intervention.
 
To be eligible, the participants should be on stable and maximally tolerated doses of either angiotensin-converting enzyme inhibitor (ACEI) or angiotensin receptor blocker (ARB) therapy, as per standard of care (SOC) and applicable guidelines, for at least 3 months. Participants must be on at least 50% of the maximum recommended dose of the ACEIs or ARB to be considered as having adequate renin-angiotensin-aldosterone system (RAAS) blockade.
 
Participants who are unable to tolerate ACEI/ARB therapy may be eligible for participation in the study, if their overall management of IgAN, including blood pressure control, is as per SOC and applicable guidelines.
 
Enrolled participants must be adults, 18 years of age or older, with IgAN diagnosis confirmed by biopsy.
 
It is anticipated that most biopsies resulting in a diagnosis of IgAN will have been interpreted using the Mesangial cellularity, endocapillary proliferation, segmental sclerosis, tubular atrophy (MEST) (Cattran et al, 2009) or MEST-C scoring system (Trimarchi, Barratt et al. 2017) from the Oxford classification of IgAN.
 
A MEST-C score finding on kidney biopsy of T2 or C2 is exclusionary for this study. If the biopsy was not reported using the Oxford classification schema, the following findings are exclusionary: a) > 50% tubular atrophy, and/or b) ≥ 25% crescents.
 
Participants must have Screening urinary protein/creatinine ratio (uPCR) ≥ 0.75 g/g or 24-hour urine protein ≥ 1.0 g/d, as measured from a 24-hour urine collection (or an intended 24-hour urine collection).
	

	
Participants must have estimated glomerular filtration rate (eGFR) ≥ 45 mL/min/1.73 m², calculated using the Chronic Kidney Disease Epidemiology Collaboration (CKD-EPI) formula (Levey, Stevens et al. 2009).
 
The study will evaluate 3 dose levels of VIS649 (2, 4, and 8 mg/kg) versus placebo. A total of 144 participants will be randomized with equal allocation (1:1:1:1) across the 4 intervention groups (approximately 36 participants per group). Randomization will be stratified first by region (Japan vs rest of world). A target of twelve or more participants are planned to be randomized in Japan; these participants will be randomized with equal allocation and without further stratification. The randomization for the rest of world will be stratified by screening uPCR (≤ 2.0 g/g vs > 2.0 g/g).
 
VIS649 or placebo will be administered as 12-monthly IV infusions starting on Day 1/Month 0. Participants will return to the study center on Day 8 and then monthly through Month 12 for safety, pharmacokinetic (PK) and/or pharmacodynamic (PD) assessments.
 
Safety assessments will include review of adverse events (AEs) (including hypersensitivity reaction and anaphylactic reaction), physical examinations, injection site tolerability (including pain, irritation and tissue damage), clinical laboratory assessments (including biochemistry, hematology, and urinalysis), laboratory testing including serum Ig levels, vital sign measurements, and use of concomitant medications.
 
Participants will return to the study center on Month 15, approximately 120 days following the last dose of study intervention (Dose 12) for additional safety, PK, PD, and efficacy assessments. Participants discontinuing dosing earlier will attend an early termination visit at the time of study intervention discontinuation and will be encouraged to attend the study visits as per schedule of assessments (SOA).
 
It is anticipated that a roll-over extension study will be designed to enable longer term therapy for randomized participants. Further details will be provided in a separate protocol.

Number of Participants:	
Approximately 144 participants. A target of twelve or more participants are planned to be randomized and enrolled in Japan. The remaining participants will be enrolled at sites in the rest of world; there are no country specific enrollment targets.

Intervention Groups and Duration:	
The study will evaluate 3 dose levels of VIS649 (2, 4, and 8 mg/kg) versus placebo. VIS649 or placebo will be administered as a single, monthly IV infusion for 12 monthly doses.
 
VIS649 will be administered IV over 1 hour, in a single, final volume 100 mL infusion in normal saline (0.9% NaCl), followed by a 25-mL saline flush. The dose of study intervention for the duration of the study will be based on the participant's Month 0 predose weight.
 
Placebo (0.9% NaCl) will be administered IV over 1 hour as a single 100 mL infusion, followed by a 25 mL saline flush.

	
An unblinded pharmacist will prepare drug or placebo for infusion. Participants, the Sponsor, the Investigator, and all other site study staff will be blinded to study intervention.
 
The total study duration for each participant (from screening to end-of-study) will be up to 16 months [assuming 1 month for screening, 12 months for twelve monthly doses (including 30 days after the twelfth dose), and a 3-month safety follow-up].

Target Population:	
Key inclusion criteria for eligibility into the study are the following:
 
 1. Participant is a male or female ≥ 18 years of age at the time of signing the informed consent. 2. Participants must have source verified biopsy-confirmed IgAN. 3. Participants has medical records showing that they have been on stable and maximally tolerated doses of either ACEI or ARB, as per SOC and applicable guidelines, for at least 3 months preceding screening. Participants should be on at least 50% of the maximum recommended dose of these agents to be considered as having adequate RAAS blockade. Participants who are unable to tolerate ACEI/ARB therapy may be eligible for participation in the study, if their overall management of IgAN, including blood pressure (BP) control, is as per SOC and applicable guidelines. 4. Participants must have screening uPCR ≥ 0.75 g/g measured from a 24-hour urine sample (or an intended 24-hour urine sample) or 24-hour urine protein ≥ 1.0 g/d, as measured from 24-hour urine sample (or an intended 24-hour urine sample). The proteinuria should be stable, defined as $< 25\%$ change when compared to values from ≥ 3 months previously (if available). If previous values are not available or if the change from a prior value is $> 25\%$, a repeat measurement of proteinuria will be done after 15 days and the participant should fulfill the above proteinuria criteria to be eligible for randomization in the study. The proteinuria should be assessed when the participant is considered to be in steady state with no recent heavy exercise, fever, or other potential issues that could impact the result. 5. Participants must have eGFR ≥ 45 mL/min/1.73 m², calculated using the CKD-EPI formula. The eGFR should be stable, as defined by a $< 25\%$ change when compared to values from ≥ 3 months previously (if available). If previous values are not available or if the change from a prior value is $> 25\%$, a repeat measurement of eGFR will be done after 15 days and the participant should fulfill the eGFR criteria to be eligible for randomization in the study. The eGFR should be measured when the participant is considered to be in a steady state without recent changes in volume status, medications that could impact the result (eg, nonsteroidal anti-inflammatory drugs [NSAIDs], aminoglycosides, co-trimoxazole) or changes in dietary protein intake.

	
6. Participant's serum Ig values must meet the criteria below:
 
 a. IgG: ≥ 700 mg/dL b. IgM: ≥ 40 mg/dL c. IgA: ≥ 70 mg/dL 
Key exclusion criteria:
 
 1. Participant has secondary forms of IgAN as defined by the treating physician (eg, Henoch-Schönlein purpura, minimal change disease with IgA deposits, infections associated with IgAN or IgAN associated with hepatic cirrhosis). 2. Participant has co-existing chronic kidney disease, other than IgAN. 3. Participant has evidence of additional pathological findings in the kidney biopsy (eg, diabetic kidney disease, membranous nephropathy, or lupus nephritis lupus). However, hypertensive vascular changes are acceptable. 4. Participant has kidney biopsy MEST or MEST-C score of T2 or C2 from the Oxford IgAN classification schema. If MEST-scoring was not performed, the presence of $> 50\%$ tubulointerstitial fibrosis, or crescents in $> 25\%$ of glomeruli is exclusionary. 5. Participant has nephrotic syndrome, defined for this purpose as 24-hour urine protein > 3.5 g with concurrent hypoalbuminemia (serum albumin < 2.5 g/dL), hyperlipidemia (total cholesterol > 350 mg/dL), and edema. 6. Participant has received a solid organ transplant, including kidney. 7. Participant has received bone marrow or hematologic stem cell transplantation 8. Participant is currently receiving systemic immunosuppression (excluding topical, ophthalmic, per rectum or inhaled corticosteroids). 9. Participant has received systemic steroids within the 12 weeks prior to initial screening. 10. Participant has received treatment with 2 or more systemic immunosuppressive agents within 2 years prior to initial screening 11. Participant has chronic infectious diseases (eg, chronic urinary tract infection, chronic sinusitis, bronchiectasis, active pulmonary or systemic tuberculosis, chronic viral hepatitis, hepatitis C virus or hepatitis B virus or HIV infection). 12. Participant has acute infectious disease at the time of screening. Participants may be rescreened following resolution of acute infection (such as urinary tract infection or respiratory tract infection), provided there is no evidence of an immunosuppressive condition that predisposed the participant to this infection. 13. Participant has Type 1 diabetes.
--	--

[figure not shown]
	
14. Patient has uncontrolled Type 2 diabetes, as evidenced by a screening hemoglobin A1c value > 8%.
 
15. Participant has uncontrolled blood pressure (> 160 mm Hg systolic or > 110 mm Hg diastolic)
 
16. Participant has a history of chronic autoimmune neurodegenerative disorders such as multiple sclerosis.
												

Data Safety Monitoring Board:
	
An independent data safety monitoring board (DSMB) will review unblinded safety data. The DSMB will meet at 5 scheduled data review meetings and on an ad hoc basis as needed. Details regarding the content and scope of safety assessments, as well as the governing of the DSMB, will be described in a separate DSMB charter.
 
Data safety monitoring board meetings will be scheduled as the following requirements are met:
 
  
 Scheduled DSMB Review	Number of Participants and Treatment Exposure	
   
 DSMB review #1	Scheduled once 12 participants have been randomized and have completed at least 3 months of dosing.	
 
 DSMB review #2	Scheduled once 24 participants have been randomized and have completed at least 3 months of dosing.	
 
 DSMB review #3	Scheduled once ~25% of participants have been randomized and have completed 3 months of dosing.	
 
 DSMB review #4	Scheduled once ~50% of participants have been randomized and have completed 6 months of dosing and ~ 20 participants have completed 12 months of dosing	
 
 DSMB review #5	Scheduled once ~50% of participants have been randomized and have completed 12 months of dosing.	
  
 
Abbreviations: DSMB = data safety monitoring board.
	Scheduled DSMB Review	Number of Participants and Treatment Exposure	DSMB review #1	Scheduled once 12 participants have been randomized and have completed at least 3 months of dosing.	DSMB review #2	Scheduled once 24 participants have been randomized and have completed at least 3 months of dosing.	DSMB review #3	Scheduled once ~25% of participants have been randomized and have completed 3 months of dosing.	DSMB review #4	Scheduled once ~50% of participants have been randomized and have completed 6 months of dosing and ~ 20 participants have completed 12 months of dosing	DSMB review #5	Scheduled once ~50% of participants have been randomized and have completed 12 months of dosing.
Scheduled DSMB Review	Number of Participants and Treatment Exposure												
DSMB review #1	Scheduled once 12 participants have been randomized and have completed at least 3 months of dosing.												
DSMB review #2	Scheduled once 24 participants have been randomized and have completed at least 3 months of dosing.												
DSMB review #3	Scheduled once ~25% of participants have been randomized and have completed 3 months of dosing.												
DSMB review #4	Scheduled once ~50% of participants have been randomized and have completed 6 months of dosing and ~ 20 participants have completed 12 months of dosing												
DSMB review #5	Scheduled once ~50% of participants have been randomized and have completed 12 months of dosing.												

Statistical Methods:
	
General Considerations
 
All data collected will be documented using summary tables, figures, and/or data listings presented by intervention and dose group. For continuous variables, descriptive statistics (number [n], mean, geometric mean and coefficient of variation [%CV], as appropriate, median, standard deviation, minimum, and maximum) will be presented. For categorical variables, frequencies and percentages will be presented. As appropriate, a 95% CI will be presented. Graphical displays may be presented.
 
Randomization and Stratification
 
Participants will be randomly assigned in a 1:1:1:1 ratio to receive VIS649 at 2, 4, or 8 mg/kg, or placebo, with approximately 36 participants randomized per intervention group. Randomization will be stratified first by region (Japan vs rest of world). Japanese participants will be randomized with equal allocation and without further stratification. Randomization for the rest of world will then
												

	
be stratified by screening uPCR (≤ 2.0 g/g vs > 2.0 g/g).
 
Interim Analysis
 
In addition to 5 DSMB safety reviews, 3 interim PK/Ig analyses and 1 interim efficacy analysis are planned. The interim PK/Ig analyses will provide additional data for population PK/PD modeling and will advise the study Sponsor on future study design and planning.
 
An interim efficacy analysis will be performed at the time of the fourth scheduled DSMB meeting (when 50% of randomized participants have completed the Month 6 visit reflecting 6 months of study intervention or placebo exposure and ~ 20 participants have completed 12 months of dosing). Group-unblinded efficacy summaries (with individual participant treatment blinded) will be prepared for Sponsor review to inform future study design.
 
The interim efficacy analysis will not include hypothesis testing and will be for the purpose of future study design and planning. The primary efficacy endpoint, change in proteinuria from baseline, will be analyzed. No modifications to this study protocol are planned based on results of the interim analyses.
 
Planned analyses
 
The primary efficacy outcome for this study is the change from baseline in uPCR on the natural log scale at Month 12. Dose response will be explored using orthogonal contrasts. Sensitivity analysis will follow using dose as a continuous covariate with associated linear, quadratic, and cubic terms.
 
In addition, to assess the dose response over time, a Mixed Model with Repeated Measurements (MMRM) which includes fixed class-effects of treatment, visit, randomization strata, and treatment by visit interaction, with a fixed effect covariate of baseline uPCR on the natural log scale will be used. An unstructured variance covariance matrix will be assumed, and linear, quadratic, and cubic dose responses will be assessed.
 
Secondary efficacy endpoints will be summarized using descriptive statistics. In addition, comparisons between dose groups against placebo will be performed using Analysis of Covariance or MMRM for continuous measures and logistic regression or generalized estimating equations for categorical variables.
 
Safety will be assessed by evaluation of AEs (including hypersensitivity reaction and anaphylactic reaction), physical examinations, injection site tolerability (including pain, irritation and tissue damage), clinical laboratory assessments (including biochemistry, hematology, and urinalysis), laboratory testing including serum Ig levels, vital signs, and concomitant medications.
 
Analysis of PK parameters will include participant data-listings of serum concentrations and summary statistics by group including means, geometric means, standard deviations, %CV, medians, and ranges, as appropriate. Summary graphs including mean concentration-time profiles by group will also be presented. For the subset of participants for whom intensive PK samples are collected, serum concentration data will be analyzed by [REDACTED].
 
[REDACTED]. In addition, [REDACTED].

--	--

	[REDACTED] as implemented in NONMEM or equivalent software. Additional analyses and summaries may be generated as appropriate.
--	--

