- M – Mesangial hypercellularity, defined as more than 3 mesangial cells in any mesangial area of a glomerulus; a score of M0 indicates hypercellularity in < 50% of glomeruli and a score of M1 is for hypercellularity noted in ≥ 50% of glomeruli.
- E – Endocapillary proliferation, defined as hypercellularity due to an increased number of cells within glomerular capillary lumina causing narrowing. E0 represents absence of hypercellularity; E1 is hypercellularity in any glomeruli.
- S – Segmental glomerulosclerosis, defined as adhesion or sclerosis (obliteration of capillary lumina by matrix) in part of but not the whole glomerular tuft; S0 represents

absence of segmental glomerulosclerosis, S1 is presence of segmental glomerulosclerosis in any glomerulus.

- T – Tubular atrophy/interstitial fibrosis, defined as the estimated percentage of cortical area showing tubular atrophy or interstitial fibrosis, whichever is greater; T0 is 0-25%; T1 is 25-50%; T2 is > 50% atrophy/interstitial fibrosis.
- C – Crescents: C0 (no crescents), C1 (crescents in < 25% of glomeruli), and C2 (crescents in ≥ 25% of glomeruli).

A MEST-C score finding on kidney biopsy of T2 or C2 is exclusionary for this study. If the biopsy was not reported using the Oxford classification schema, the following findings are exclusionary: a) > 50% tubular atrophy, and/or b) ≥ 25% crescents.

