5.2 Exclusion Criteria

Participants are excluded from the study if they meet any of the following criteria:

1. Participant has secondary forms of IgAN as defined by the treating physician (eg,, Henoch-Schönlein purpura, minimal change disease with IgA deposits, infection associated IgAN or IgAN associated with hepatic cirrhosis).
2. Participant has co-existing CKD, other than IgAN.
3. Participant has evidence of additional pathological findings in the kidney biopsy (eg, diabetic kidney disease, membranous nephropathy or lupus nephritis lupus). However, hypertensive vascular changes are acceptable.
4. Participant has kidney biopsy MEST or MEST-C score of T2 or C2 from the Oxford IgAN classification schema. If MEST-scoring was not performed, the presence of $> 50\%$ tubule-interstitial fibrosis or crescents in $> 25\%$ of glomeruli is exclusionary.
5. Participant has nephrotic syndrome, defined for this purpose as 24-hour urine protein > 3.5 g with concurrent hypoalbuminemia (serum albumin < 2.5 g/dL), hyperlipidemia (total cholesterol > 350 mg/dL) and edema.
6. Participant has received a solid organ transplant, including kidney.
7. Participant has received bone marrow or hematologic stem cell transplantation.
8. Participant is currently receiving systemic immunosuppression (excluding topical, ophthalmic, per rectum or inhaled corticosteroids).
9. Participant has received systemic steroids within the 12 weeks prior to initial screening.
10. Participant has received treatment with 2 or more systemic immunosuppressive agents within 2 years prior to initial screening.
11. Participant has chronic infectious diseases (eg, chronic urinary tract infection, chronic sinusitis, bronchiectasis, active pulmonary or systemic tuberculosis, chronic viral HCV or hepatitis B virus or HIV infection).

12. Participant has a known allergy or intolerance to any component of the study intervention.
13. Participant has acute infectious disease at the time of screening. Participants may be rescreened following resolution of acute infection (such as urinary tract infection or respiratory tract infection), provided there is no evidence of an immunosuppressive condition that predisposed the participant to this infection.
14. Participant has Type 1 diabetes.
15. Participant has uncontrolled Type 2 diabetes, as evidenced by a screening hemoglobin A1c value > 8%.
16. Participant has uncontrolled blood pressure (> 160 mm Hg systolic or > 110 mm Hg diastolic).

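### As worded, the crescent exclusion does not reach a biopsy reported with MEST but without a C grade

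*Protocol*

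**What the plan says.** The rule appears four times in the protocol, in two forms.

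- **Exclusion 4, Section 5.2 and synopsis.** The first limb, and the condition that opens the second, read "Participant has kidney biopsy MEST or MEST-C score of T2 or C2 from the Oxford IgAN classification schema. If MEST-scoring was not performed". The second limb, which applies only in that case, adds a tubulointerstitial fibrosis limit and "crescents in $> 25\%$ of glomeruli is exclusionary".
- **Design text, Section 4.1 and synopsis (Overall Design).** The first limb is "A MEST-C score finding on kidney biopsy of T2 or C2 is exclusionary for this study". The second limb opens "If the biopsy was not reported using the Oxford classification schema, the following findings are exclusionary" and lists tubular atrophy above 50% and crescents at or above 25%.

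Section 4.1 defines the top crescent grade as "C2 (crescents in ≥ 25% of glomeruli" and lists C among the components of MEST-C.

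**The concern.** In each form the first limb tests a grade and the second tests a raw percentage when there is no grade. The switch between limbs asks whether the biopsy was scored at all, not whether crescents were scored. A report that has M, E, S and T but no C counts as scored, so the raw crescent percentage is never consulted.

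The protocol excludes this finding for the report types on either side, so the omission looks unintended. A participant admitted this way has a one-in-four chance of 12 months on placebo. Section 6.5.1 prohibits systemic corticosteroids and other immunosuppression during the study; if the investigator judges such therapy necessary, the sponsor is notified and study dosing may be discontinued. With about 80 sites, eligibility could also turn on how each site reads the sentence.

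**Working it through.** The plan gives no figure on this point and no arithmetic applies. The check sets the statements side by side and runs one case through them.

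1. **What each report contains.** The synopsis spells out the older score as "Mesangial cellularity, endocapillary proliferation, segmental sclerosis, tubular atrophy (MEST": four components, no crescents. Crescents enter only with MEST-C. The protocol treats both as Oxford scores.

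2. **Whether MEST-only reports are expected.** The synopsis says "It is anticipated that most biopsies resulting in a diagnosis of IgAN will have been interpreted using the" MEST or MEST-C systems, and exclusion 4 names both. The protocol cites them to 2009 and 2017 publications respectively. Neither inclusion 2 (Section 5.1) nor footnote 4 of the schedule of assessments limits biopsy age. SAP Section 4.2 plans to tabulate time since biopsy and the scoring method. MEST-only reports are therefore a foreseen input.

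3. **Test case.** Take a biopsy with crescents well above 25% of glomeruli and T0 or T1.

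| Report type | Exclusion 4 (5.2, synopsis) | Design text (4.1, synopsis) | Outcome as written |
|---|---|---|---|
| MEST-C | C2 recorded | C2 recorded | Excluded |
| MEST without C | No C grade; fallback off because MEST scoring was done | No C grade; fallback off because the report is Oxford | Not excluded |
| Not Oxford-scored | Fallback on | Fallback on | Excluded |

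Only the middle row escapes, and it does so under both forms.

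4. **The same test for T2.** Exclusion 4 names MEST as well as MEST-C, so T2 on a MEST-only report is caught. The gap is confined to crescents.

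5. **Other criteria.** No other inclusion or exclusion criterion mentions crescents. Exclusion 24 is discretionary and concerns illnesses not already listed. Section 8 has the pathology report submitted to confirm the diagnosis; it does not ask anyone to derive a C grade.

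6. **Whether the analysis would pick it up.** A participant admitted this way breaches no written criterion, so the per-protocol definition in SAP Section 2.1 would not remove them on eligibility. Randomisation is stratified by region and, outside Japan, by screening uPCR. The subgroup list in SAP Section 4.3.2 contains no histological factor.

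**The case against.** The best reply is that the text is loose about labels and a strictly literal reading is a poor guide to site practice. Section 4.1 defines C2 by histology, so a site holding a MEST-only report that states a crescent percentage could apply the definition and record C2. Section 4.1 names only MEST-C, so read just as literally it would let T2 through on a MEST-only report, which exclusion 4 shows is not meant. Biopsy review is a screening procedure with source-verified documentation, and SAP Section 4.2 tabulates crescents, so a high count in the report would be visible.

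This stands in part. A reader might infer that a MEST-only biopsy can never be treated as C2; the documents do not support that, because the definition is there for a site to apply. But no passage tells the site to apply it, and seeing a crescent count is not the same as having a rule that acts on it.

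The reply also says that other criteria narrow the group. Inclusion 5 requires eGFR of at least 45 mL/min/1.73 m². Inclusions 4 and 5 require stable proteinuria and eGFR, or a qualifying repeat measurement. Exclusions 8 to 10 remove current systemic immunosuppression, recent systemic steroids, and two or more immunosuppressive agents within two years. That is fair, and it limits the size of the problem, although none of these criteria addresses crescents. An old crescent count also does not establish current crescentic disease, so a reader should not conclude that actively crescentic participants will be randomised.

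**Conclusion.** The point holds on the wording. As written, a MEST-only report meets neither crescent test, so the protocol does not exclude a finding that it excludes for MEST-C and for unscored biopsies. The conclusion rests on two readings: that MEST has the four components the protocol gives it, and that a MEST report counts as both scored and Oxford.

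The size is unknown. The documents give neither the share of biopsies reported without C nor the frequency of crescents among them, so any count out of 144 would come from assumed inputs; the number is probably small. A reader might also infer that such participants would stop treatment more often or add noise to Month 12 uPCR. Nothing in the documents supports that, and the point does not need it. This is an eligibility rule that should be corrected because it is incomplete and open to inconsistent application, not because it threatens the primary analysis.

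**What to change.** Reconcile exclusion 4 (Section 5.2 and synopsis) with the design text (Section 4.1 and synopsis) so that the existing crescent check applies whenever no C grade is reported, and say expressly that this includes MEST-only reports. The two fallback forms already conflict on the threshold (> 25% in exclusion 4, ≥ 25% in the design text) and on the tubular term (tubulointerstitial fibrosis against tubular atrophy). The sponsor should settle these in the same edit and use the resulting single crescent threshold here; which value is right is not for this review. Add the check to the eligibility form.

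The cost is one clause and one form item. Pathology reports are already submitted with the eCRFs, so no new data are needed. The downside is possibly a few more screen failures.

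If enrolment is complete, use the baseline scoring-method and crescent fields in SAP Section 4.2, with the filed pathology reports where the crescent field is blank, to identify affected participants and report how many there are in each arm.
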